11.2 CLINICAL LABORATORY PARAMETERS

Descriptive statistics for clinical laboratory values and change from baseline values at each assessment timepoint will be presented for the OLTP and by treatment group for the DBTP in International System of Units (SI units). There is a central lab transition (from Q2 to Covance) during the clinical trial. In addition, descriptive statistics for clinical laboratory values and changes from baseline values at each assessment timepoint will also be presented by central lab for the OLTP and by treatment group for the DBTP in SI units.

The descriptive statistics will be provided for the following laboratory parameters:

Hematology	Absolute and differential white blood cell count, erythrocyte count, hemoglobin, hematocrit, platelet count, and red blood cell indices (mean corpuscular volume, mean corpuscular hemoglobin, and mean corpuscular hemoglobin concentration)
Fasting serum chemistry	Sodium, potassium, calcium, chloride, bicarbonate, glucose, blood urea nitrogen, creatinine, total protein, alkaline phosphatase, albumin, total bilirubin, direct bilirubin, indirect bilirubin, AST, ALT, Free T3, free T4, TSH, lactate dehydrogenase, creatine phosphokinase, γ -glutamyl transpeptidase, uric acid, phosphate, lipid panel (total cholesterol, triglycerides, low density lipoproteins, high density lipoproteins), prolactin, insulin, and magnesium
Urinalysis	Specific gravity, pH, protein, glucose
Hemoglobin A_{1c}	

In addition, descriptive statistics for values and changes from the baseline values in conventional units at each assessment time point will be presented for selected clinical laboratory parameters listed in [Appendix III](#). A description of reporting the lab values in conventional units in patient narratives (along with the standard reporting in SI units) is presented at the end of [Appendix III](#). Only patients with selected clinical laboratory data at baseline and at least one postbaseline visit during the OLTP and DBTP will be included in the summary.

Clinical laboratory test values will be considered potentially clinically significant (PCS) if they meet either the lower-limit or higher-limit PCS criteria listed in [Table 11.2-1](#). The number and percentage of patients who have PCS postbaseline clinical laboratory values will be tabulated overall for the OLTP, and by treatment group for the DBTP. The percentages will be calculated relative to the number of patients with available non-PCS baseline values and at least 1 postbaseline assessment for the corresponding treatment periods (OLTP or DBTP). The numerator will be the total number of patients with available non-PCS baseline values and at least 1 PCS postbaseline value for the corresponding treatment periods (OLTP or DBTP). A supportive tabular display of patients with PCS postbaseline values will be provided, including the PID number, study center number, and baseline and all postbaseline (including non-PCS) values.

In addition, a tabular display showing all AEs that occurred in patients who had PCS postbaseline clinical laboratory values will be provided.

Potential Hy's Law criteria within a 24-hour window is defined by a post baseline elevation of alanine aminotransferase (ALT) or aspartate aminotransferase (AST) $\geq 3x$ ULN, along with total bilirubin (TBL) $\geq 2x$ ULN and a non-elevated alkaline phosphatase (ALP) $< 2x$ ULN, all based on blood draws collected within a 24-hour period.

Patients who meet the potential Hy's Law criteria during the OLTP will be summarized for the OL Safety Population. Patients who meet the potential Hy's Law criteria from the first dose of DB IP to within 30 days after the last dose of DB IP will be summarized for the DB Safety Population. Supportive tabular displays will also be provided.

[figure not shown]
The number and percentage of patients with treatment-emergent significant changes in lipids parameters (total cholesterol, LDL cholesterol, HDL cholesterol, and triglycerides) and glucose will be tabulated by treatment group for the OLTP and the DBTP. The criteria for treatment-emergent significant changes in lipids and glucose are specified in [Table 11.2-2](#) and [Table 11.2-3](#). Percentages will be calculated relative to the number of patients with baseline values meeting the specified baseline criteria and with at least one postbaseline assessment during the specific period. The change in lipids and glucose from baseline to the highest (lowest for HDL cholesterol) postbaseline measurement during the specific period will be summarized. Supportive listings of patients with treatment-emergent changes in lipids and glucose values will be provided.

[figure not shown]

Cariprazine
RGH-MD-25 – Statistical Analysis Plan
Amendment #3 – 23 November 2022

Cariprazine
RGH-MD-25 – Statistical Analysis Plan
Amendment #3 – 23 November 2022

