4.1 Number of Patients

Approximately 378 patients are planned to be randomized (126 per treatment arm). It is anticipated that approximately 1245 patients will be screened and approximately 822 will enter the OL treatment period. In the event that screening or randomization failure rates are higher than projected, enrollment will continue until approximately 126 patients per treatment arm are randomized. Screened patients who have not reached the randomization visit at the time the randomization target is met, will not be discontinued from the study. These patients will be allowed to continue in the study until they either complete the study, prematurely discontinue, or otherwise fail to meet randomization criteria.

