9.5 Potential Hy's Law Cases

Criteria for potential Hy's Law cases are as follows:

- ALT or AST \geq 3 × ULN AND
- Total bilirubin $\geq 2 \times ULN AND$
- Alkaline phosphatase < 2 × ULN

Study site personnel must report every patient who meets these 3 criteria. Typically, all 3 analytes will be obtained from the same sample, but they may come from multiple samples taken within a 24-hour period. This requirement applies from the time the patient signs the ICF for the trial until 30 days after the final protocol-defined study visit or the last known dose of IP (if the final visit does not occur).

A lab alert for potential Hy's Law cases will be in place, and will notify investigators and the sponsor immediately when the above criteria have been met. A potential Hy's Law case must be faxed to the sponsor on the SAE/AESI form as soon as possible (within 24 hours of learning of the potential Hy's Law) to the following SAE/pregnancy fax number/email address even if no AE has occurred:

[contact] (back-up [contact])

Email: [contact]

The eCRF pages for potential Hy's Law cases must be completed within 7 calendar days. Every effort to determine the cause of the liver enzyme abnormalities must be made, and close monitoring must be initiated in conjunction with the study physician and in accordance with the FDA "Guidance for Industry: Drug-Induced Liver Injury-Pre-Marketing Clinical Evaluation" July 2009.

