12.13.5 Visit 31/ET- End of Double-Blind and Early Termination Visit

Every attempt should be made to complete the Visit 31/ET efficacy and safety assessments on the same date. In the event that a remote visit for Visit 31/ET is not possible at the scheduled timepoint, all Visit 31/ET efficacy assessments should be completed within 2 weeks of last dose of IP. If Visit 31/ET is completed as a remote visit without the assessment of clinical laboratory parameters (including pregnancy testing, if applicable), physical examination and/or ECG, the patient should be brought back for safety assessments during the SFU period. Patients who have missed the safety assessments scheduled for Visit 31/ET and are unable to return for these assessments during the SFU period should be encouraged to return to the site for a final assessment of safety when possible. All attempts should be made to make a final assessment of safety even if it falls beyond the end of the Safety Follow-up period. If Visit 31/ET procedures are being completed more than 2 weeks after the last dose of IP, efficacy assessments should be omitted.

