6.4 OPEN-LABEL SAFETY-FOLLOW-UP POPULATION

The OL SFU population will consist of patients in the OL safety population who were not randomized.

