7.0 STUDY PATIENTS

7.1 PATIENT DISPOSITION

The OLTP starts with the first dose of OLTP and ends with one of the following: the last scheduled assessment at Visit 12 (Week 16) or early termination (ET) before Visit 12 for patients who do not enter the DBTP; or 1 day before the date of the first dose of DBTP (or the date of the first dose of the DB IP if the last scheduled assessment date in the OLTP is on the date of the first dose of the DBTP) for patients who enter the DBTP.

The DBTP starts with the first day of randomization and ends with the last scheduled assessment at Visit 31 (Week 55) or ET.

The SFU period starts one day after the end of the previous period and ends with the last available assessment. For patients without Visit 32 (Week 57) or Visit 34 (Week 59) assessment, the SFU period would not be derived.

Screen-failure patients (ie, patients screened but not included in the OL Safety Population) and the associated reasons for failure will be tabulated overall for the Screened Population.

The number and percentage of patients in the Screened, OL Safety and OL ITT Populations will be summarized overall and by study center. The number and percentage of patients in the Randomized, DB Safety, and DB ITT Populations will be summarized overall by treatment group and by treatment group and study center.

The number and percentage of patients in the OL Safety Population, who prematurely discontinued from the OLTP, who completed the OLTP, who entered the DBTP, and who entered the SFU period will be summarized overall and by reasons for premature discontinuation as recorded on the OL disposition page of the electronic case report forms (eCRF).

Similarly, the number and percentage of patients in the DB Safety Population who completed the DBTP, who prematurely discontinued from the DBTP, and who entered the SFU period will be summarized overall, by DBTP treatment group and by reasons for premature discontinuation as recorded on the DB disposition page of the eCRF. Patients who relapse during the DBTP will also be summarized as completing the study.

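### SAP 11.2 counts potential Hy's Law cases to 30 days after last dose in double-blind patients but only to the Visit 12/ET assessment in patients who never start double-blind drug, so a case first detected in their safety follow-up is in neither summary

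*SAP*

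**What the plan says.** SAP 11.2 defines a potential Hy's Law case as raised ALT or AST with raised total bilirubin and alkaline phosphatase below 2 × ULN, all within 24 hours. It then gives two counting rules.

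- Open-label: "Patients who meet the potential Hy's Law criteria during the OLTP will be summarized for the OL Safety Population".
- Double-blind: cases arising "from the first dose of DB IP to within 30 days after the last dose of DB IP" are summarized for the DB Safety Population.

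SAP 7.1 fixes where the open-label period stops. For patients who are not carried forward it is the Visit 12 assessment or "early termination (ET) before Visit 12 for patients who do not enter the DBTP". What follows belongs to safety follow-up (SFU): "The SFU period starts one day after the end of the previous period and ends with the last available assessment". SAP 6.4 defines a population for that stage: "The OL SFU population will consist of patients in the OL safety population who were not randomized".

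The protocol's reporting duty is wider. Section 9.5 makes sites report every potential case from consent "until 30 days after the final protocol-defined study visit", or to 30 days after the last known dose if that visit does not occur. It draws no line between open-label and double-blind patients.

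The protocol also provides for laboratory tests after ET. Section 8.4.7 lets the investigator order them as needed in SFU, and allows the period to be used to follow up abnormal findings from either treatment period. Under the COVID-19 provisions (Section 12.13.5), when a remote ET visit is done without the laboratory panel, the "patient should be brought back for safety assessments during the SFU period". Table 5, footnote b, says the same of the Visit 31/ET laboratory tests.

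**The concern.** The two counting rules stand in adjacent sentences, serve the same purpose, and end differently. The double-blind rule follows the patient off drug; the open-label rule stops with the period. No reason is given. The SAP amendment log says only that the summary was added to evaluate liver function tests.

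The narrower rule is also out of line with the rest of the safety plan. SAP 11.0 names the open-label SFU period as a reporting period, and the SAP uses it for ocular events and vital signs; Section 11.1 also tabulates treatment-emergent adverse events for it. The Hy's Law count is not carried into it.

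At stake is a rare-event count in which one omitted case changes the result from none to some. A patient taken off open-label drug with an evolving liver abnormality is a natural candidate for discretionary tests in SFU. If the combined criteria are first met then, the planned summary does not show it.

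**Working it through.** **Step 1. Follow individual patients through the rules.**

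| Patient and laboratory result | Open-label summary | Double-blind summary |
|---|---|---|
| Takes no DB drug; criteria met on the on-site Visit 12/ET panel, even if drawn after stopping drug | Counted: the period closes with that assessment | Not applicable |
| Takes no DB drug; criteria first met on an unscheduled SFU test | Not counted: after the OLTP | Not counted: not in the DB Safety Population |
| Takes no DB drug; remote ET visit, make-up panel in SFU | Not counted, for the same reason | Not counted |
| Took DB drug; criteria met in SFU within 30 days of last dose | Not applicable | Counted |

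Rows two and three are the gap. No chemistry is scheduled at Visits 32 or 33 for anyone (Protocol Table 3 and Section 8.4.7), so the gap consists only of unscheduled and make-up tests.

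**Step 2. Check whether another planned output would show the case.**

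- The tables of potentially clinically significant laboratory values in SAP 11.2 are tied to the OLTP or DBTP. SAP 16.3 uses all postbaseline values to judge them and lists all assessments, but those are single-parameter criteria, not the combined one.
- Adverse event tables and listings show the case only if an event was recorded. Protocol 9.5 requires a report even without one.

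So no other planned output is certain to show it as a Hy's Law case.

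**Step 3. Size the population with the uncovered window.**

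Inputs: 378 randomized, 822 entering open-label treatment and 1245 screened (Protocol 4.1); 882 entering open-label treatment, 46% reaching randomization and 34% screen failure (SAP 14.0).

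Reproducing the planned number treated:

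- 378 / 0.46 = 821.7, and 1245 × (1 − 0.34) = 821.7. Both give 822.
- 882 does not fit: 378 / 882 = 42.9%, not 46%, and 882 / 0.66 = 1336 screened, not 1245.

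Patients not randomized:

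- Protocol figure: 822 − 378 = 444; 444 / 822 = 54.0%.
- SAP figure: 882 − 378 = 504; 504 / 882 = 57.1%.

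These counts assume that every randomized patient takes double-blind drug. Any who do not would add slightly to them.

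**Step 4. Show what that could mean in cases.**

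The documents give no Hy's Law rate, so the rate of first meeting the criteria after ET is an assumption. Expected cases = patients × rate; chance of at least one = 1 − (1 − rate)^patients.

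| Assumed rate | Expected, n = 444 | Chance of at least one | Expected, n = 504 | Chance of at least one |
|---|---|---|---|---|
| 0.01% | 0.04 | 4% | 0.05 | 5% |
| 0.1% | 0.44 | 36% | 0.50 | 40% |
| 0.5% | 2.2 | 89% | 2.5 | 92% |

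Even at the top of this range only two or three cases are expected.

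**The case against.** The best case against the point is that very little falls through.

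- **The ET panel is counted.** It includes ALT, AST, bilirubin and alkaline phosphatase, and the cut-off is that assessment, not the last dose. This stands. A reader might infer that all 30 days after last dose are excluded for more than half the treated patients; SAP 7.1 does not support that.
- **Liver-related withdrawals are confirmed before ET.** Protocol 8.9 makes repeat testing part of the trigger for discontinuation, so confirmation normally falls inside the OLTP. This stands, and the repeat-test requirement is not evidence that liver tests occur in SFU. The evidence is Sections 8.4.7 and 12.13.5, and the latter applies only under pandemic restrictions.
- **Cases reach the sponsor anyway.** Section 9.5 requires a report within 24 hours and dedicated eCRF pages, whatever the period. This stands as to site reporting and case review. It does not put the case into the planned count.
- **No comparison is biased.** The open-label stage is uncontrolled and the three randomized arms share one window. This stands; no efficacy result or between-arm safety comparison is affected.
- **The visit-window tables in SAP 16.1, including the one for SFU, are not legible in the public text.** How late tests are mapped to a period cannot be fully checked. The conclusion rests on the period definitions in SAP 7.1.

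**Conclusion.** The point holds as a gap in one safety summary. For patients who take no double-blind drug, a potential Hy's Law case first detected after the Visit 12/ET assessment is in neither summary, although the protocol requires it to be reported. The uncovered window applies to about 444 of 822 planned treated patients (54%), or 504 of 882 (57%). "Over half" is therefore right only as a share of patients with an uncovered stretch of follow-up.

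It would be tempting to read this as liver cases being lost in over half the patients. The documents do not support that: no chemistry is scheduled in SFU, the ET panel is counted, and few or no cases are likely. The conclusion assumes that the SAP 7.1 period boundaries govern the Hy's Law count. It is a small point, but worth correcting because the count concerns a rare and serious signal and should follow one rule for all treated patients.

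Separately, 822 and 882 should be reconciled; only 822 agrees with the stated 46%, 34% and 1245.

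**What to change.** In the open-label sentence of SAP 11.2, insert after OLTP: *or, for patients who take no DB IP, from the first OL dose up to 30 days after the last OL dose (or through the Visit 12/ET assessment, if later)*. Apply the same window to the supporting displays.

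Three features of the wording matter.

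- Defining the group by taking no DB drug also covers patients randomized but never dosed, who are outside both the DB Safety Population (SAP 6.6) and the OL SFU population (SAP 6.4).
- The clause about a later Visit 12/ET assessment keeps every result that the present rule counts.
- For patients who do start DB drug, the boundary between the two counts stays where SAP 7.1 puts it, so the change adds no new shared day.

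The cost is one clause and a small addition to a safety summary, with no new data collection. Two limits remain. Results from alternate laboratories are held only in source documents (Protocol 12.13.4.2) and would still not be captured. The 30-day limit matches the double-blind rule but is shorter than the reporting period in Protocol 9.5, which runs from the final visit when that visit takes place.

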11.3 VITAL SIGNS

Descriptive statistics (n, mean, standard deviation, median, minimum and maximum) for vital signs (supine systolic and diastolic blood pressures, supine pulse rate, weight, BMI, waist circumference, and temperature) and changes from baseline values at each visit and at the end of study will be presented overall for the OLTP and OL SFU period, and by treatment group for the DBTP and DB SFU period.

Vital sign values will be considered as PCS if they meet both the observed-value criteria and the change-from-baseline criteria listed in [Table 11.3-1](#). The number and percentage of patients with PCS postbaseline values will be tabulated overall for the OLTP and by treatment group for the DBTP. The percentages will be calculated relative to the number of patients with available baseline values and at least 1 postbaseline assessment for the corresponding periods (OLTP or DBTP). The numerator will be the total number of patients with available baseline values and at least 1 PCS postbaseline value for the corresponding periods (OLTP or DBTP). A supportive tabular display of patients with PCS postbaseline values will be provided, including the PID number, study center number, and baseline and all postbaseline (including non-PCS) values.

In addition, a tabular display showing all Aes that occurred in patients who had PCS postbaseline vital sign values will be provided.

The number and percentage of patients with orthostatic hypotension will be provided for OLTP and DBTP. Orthostatic hypotension is defined as a reduction of ≥ 20 mm Hg in systolic blood pressure or a reduction of ≥ 10 mm Hg in diastolic blood pressure while changing from the supine to standing position. A supportive listing of patients with orthostatic hypotension will be provided. A listing of all AEs for patients with orthostatic hypotension will also be provided.

Table 11.3-1. Criteria for Potentially Clinically Significant Vital Signs

Parameter	Flag	Criteria^a	
		Observed Value	Change From Baseline
Supine systolic blood pressure, mm Hg	High	≥ 180	Increase of ≥ 20
	Low	≤ 90	Decrease of ≥ 20
Supine diastolic blood pressure, mm Hg	High	≥ 105	Increase of ≥ 15
	Low	≤ 50	Decrease of ≥ 15
Supine pulse rate, bpm	High	≥ 120	Increase of ≥ 15
	Low	≤ 50	Decrease of ≥ 15
Weight, kg	High	—	Increase of $\geq 7\%$
	Low	—	Decrease of $\geq 7\%$

a A postbaseline value is considered potentially clinically significant if it meets both the observed-value and the change-from-baseline criteria.

bpm = beats per minute.

As specified in the Seventh Report for the Joint National Committee on prevention, detection, evaluation and treatment of high blood pressure ([NIH Publication No. 04-5230, 2004](#)), hypertension status is defined in the following texts.

- Normotensive: systolic BP < 120 mm Hg and diastolic BP < 80 mm Hg.

- Prehypertension: systolic BP 120 to 139 mm Hg or diastolic BP 80 to 89 mm Hg
- Stage I Hypertension: systolic BP 140 to 159 mm Hg or diastolic BP 90 to 99 mm Hg
- Stage II Hypertension: systolic BP \geq 160 mm Hg or diastolic BP \geq 100 mm Hg

The number and percentage of patients with hypertension status changes from baseline will be provided for

- Shift of hypertension status from baseline to end of the OLTP in the OL Safety Population
- Shift of hypertension status from baseline to highest category during the OLTP in the OL Safety Population
- Shift of hypertension status from baseline to end of the DBTP in the DB Safety Population
- Shift of hypertension status from baseline to highest category during the DBTP in the DB Safety Population

Supportive listings of patients who have a shift in hypertension status from normotensive/prehypertension at Baseline to stage I/stage II hypertension will be provided.

11.4 ELECTROCARDIOGRAM

Descriptive statistics (n, mean, standard deviation, median, minimum and maximum) for ECG parameters (heart rate, RR interval, PR interval, QRS duration, QT interval, and QTc) and changes from baseline values at each assessment time point to the end of study will be presented overall for the OLTP and by treatment group for the DBTP. The QTc will be calculated using both the Bazett and Fridericia corrections.

ECG parameter values are considered PCS if they meet or exceed the higher-limit PCS criteria listed in [Table 11.4-1](#). The number and percentage of patients with PCS postbaseline ECG values will be tabulated overall for the OLTP and by treatment group for the DBTP. The percentages will be calculated relative to the number of patients with available non-PCS baseline values and at least 1 postbaseline assessment for the corresponding periods (OLTP or DBTP). The numerator is the total number of patients with available non-PCS baseline values and at least 1 PCS postbaseline value for the corresponding periods (OLTP or DBTP). A supportive tabular display of patients with PCS postbaseline values will be provided, including the PID number, study center number, baseline, all postbaseline (including non-PCS) values, and change from baseline.

In addition, a tabular display showing all AEs that occurred in patients who had postbaseline PCS ECG values will be provided.

A shift table from baseline to the end of study in the Investigator's overall interpretation of the ECG will be presented overall for the OLTP and by treatment group for the DBTP for the following categories: normal; abnormal, not clinically significant; abnormal, clinically significant. A listing of patients with postbaseline clinically significant ECG abnormalities according to the Investigator's or by the central cardiologist's overall interpretation will be provided.

The number and percentage of patients with an increase > 30 msec but ≤ 60 msec, and with an increase > 60 msec in QTcB or QTcF will be tabulated. Patients will be counted only once for the most severe category. A supportive listing of patients with postbaseline QTcB or QTcF increases > 30 msec will be provided, including the PID number, study center, and all QTc values (including changes from baseline). A listing of all AEs for patients with postbaseline QTcB or QTcF increases > 30 msec will also be provided.

Table 11.4-1. Criteria for Potentially Clinically Significant Electrocardiograms

Parameter	Unit	Higher Limit
QRS duration	msec	≥ 150
PR interval	msec	≥ 250
QTcB	msec	> 500
QTcF	msec	> 500

QTcB = QT interval corrected for heart rate using the Bazett formula $QT/ (RR)^{1/2}$; QTcF = QT interval corrected for heart rate using the Fridericia formula ($QTcF = QT/ (RR)^{3/2}$).

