6.6.5 Electrocardiograms

A 12-lead ECG will be performed at Screening (Visit 1), Visit 12 and Visit 31 or ET using a standard paper speed of 25 mm/sec. ECGs will be electronically transmitted for analysis according to the instructions provided by the ECG central reader. Measurements (in msec) will be recorded for the following parameters in lead II or lead III (other leads may be used only if it is not possible to obtain good-quality tracings from lead II or lead III): PR interval, QRS interval, RR interval (preceding the QT), and uncorrected QT interval. Copies of the ECG waveforms will also be sent to the central reader, where the ECG parameters will be measured and evaluated. The ECG tracing and cardiology report will be retained as a source document.

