7.3.4.4 Electrocardiogram

Descriptive statistics for ECG parameters (ie, heart rate, PR interval, QRS interval, RR interval, QT interval, QTcB, and QTcF) and changes from baseline values at each assessment time point in this study will be presented.

[figure not shown]
The number and percentage of patients with postbaseline PCS ECG values will be tabulated by treatment group for the DB treatment period. The criteria for PCS ECG values will be detailed in the statistical analysis plan. The percentages will be calculated relative to the number of patients with available non-PCS baseline values and at least 1 postbaseline assessment for the DB treatment period. The numerator will be the total number of patients with available non-PCS baseline values and at least 1 postbaseline PCS value for the DB treatment period. A supportive tabular display of patients with postbaseline PCS values will be provided, including the PID number, baseline, all postbaseline (including non-PCS) values, and change from baseline. In addition, a tabular display showing all AEs that occurred in patients who had postbaseline PCS ECG values will be provided.

A shift table from baseline to the end of study in the investigator's overall interpretation of the ECG will be presented by treatment group for the following categories: normal; abnormal, not clinically significant; abnormal, clinically significant. A tabular display showing patients with postbaseline clinically significant ECG abnormalities according to the investigator's overall interpretation will be provided.

The number and percentage of patients with a change from baseline QTc > 30 msec but not exceeding 60 msec and of patients with an increase > 60 msec will be tabulated by treatment group. A supportive listing that includes PID number, study center number, all QTc values (including change from baseline values), and all AEs will be provided for all patients with postbaseline QTc changes > 30 msec.

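### The SAP's only QTcF formula is labelled Fridericia but prints RR to the power 3/2 instead of 1/3

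*SAP*

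**What the plan says.** SAP Section 11.4 sets the method by name: "The QTc will be calculated using both the Bazett and Fridericia corrections". The footnote to Table 11.4-1 then prints both formulas. Bazett has an RR exponent of 1/2: "QTcB = QT interval corrected for heart rate using the Bazett formula $QT/ (RR)^{1/2". The other reads "QTcF = QT interval corrected for heart rate using the Fridericia formula ($QTcF = QT/ (RR)^{3/2", an exponent of 3/2. The footnote gives no unit for RR.

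QTcF feeds several outputs in SAP 11.4:
- the descriptive statistics;
- the potentially clinically significant (PCS) table, with the limit "QTcF msec > 500";
- the change categories above 30 and above 60 msec, of which the upper one is worded "with an increase > 60 msec in QTcB or QTcF will be tabulated";
- the supporting patient and adverse-event listings.

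Protocol 7.3.4.4 names the parameters without formulas: "heart rate, PR interval, QRS interval, RR interval, QT interval, QTcB, and QTcF". Protocol 6.6.5 gives the unit of the recorded intervals: "Measurements (in msec) will be recorded for the following parameters in lead II or lead III". It lists them as "PR interval, QRS interval, RR interval (preceding the QT), and uncorrected QT interval", so QTc is not among them.

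**The concern.** The name and the formula in the footnote disagree. They give the same number only when RR is exactly 1 second (60 bpm). Because no other QTcF formula exists in either document, the footnote is what a programmer or an independent checker would find when looking up the derivation.

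If the footnote were followed as printed, QTcF would rise steeply with heart rate. Patients with unremarkable QTcF would be flagged at ordinary rates, and real prolongation would be hidden at slow rates. Small heart-rate shifts between baseline and follow-up would appear as large QTcF changes. The PCS percentages count only patients whose baseline is not PCS, so false flags at baseline would also remove patients from the denominator.

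The missing RR unit is a second gap. Intervals are recorded in msec, but both corrections need RR in seconds to give a value comparable with 500 msec.

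**Working it through.** **Inputs.** The exponents 1/2 (Bazett) and 3/2 (as printed) come from the SAP Table 11.4-1 footnote. The exponent 1/3 is the definition of the named Fridericia method. The limits of 500, 30 and 60 msec come from SAP 11.4. The documents give no QT or heart-rate values, so those below are illustrative assumptions. RR = 60/HR, in seconds.

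**Single ECGs**

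| QT (msec) | HR (bpm) | RR (s) | QTcB, RR^(1/2) | QTcF, RR^(1/3) | As printed, RR^(3/2) |
|---|---|---|---|---|---|
| 380 | 60 | 1.000 | 380 | 380 | 380 |
| 380 | 70 | 0.857 | 410 | 400 | 479 |
| 380 | 75 | 0.800 | 425 | 409 | 531 |
| 380 | 80 | 0.750 | 439 | 418 | 585 |
| 540 | 50 | 1.200 | 493 | 508 | 411 |
| 530 | 55 | 1.091 | 507 | 515 | 465 |

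For example, 380/0.8^(1/3) = 409.3 and 380/0.8^(3/2) = 531.1; 540/1.2^(1/3) = 508.2 and 540/1.2^(3/2) = 410.8. In the 50 bpm case QTcB is 493.0, so the QTcB limit does not catch the patient either.

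**When a false or missed flag occurs.** Let F be the cube-root QTcF. Then QT = F × RR^(1/3), and the printed value is F × RR^(1/3 − 3/2) = F × RR^(−7/6). This exceeds 500 when RR < (F/500)^(6/7).

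| F (msec) | Printed value exceeds 500 when HR is above |
|---|---|
| 390 | 74.2 bpm |
| 400 | 72.6 bpm |
| 410 | 71.1 bpm |
| 420 | 69.7 bpm |
| 430 | 68.3 bpm |

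For F = 510, a true exceedance, the printed value falls below 500 when HR is under 59.0 bpm.

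**Change categories, with true QTcF unchanged**
- F = 410, from 65 to 75 bpm: QT goes from 399.2 to 380.6. The printed value goes from 450.1 to 531.9, a change of +81.8, counted as above 60. QTcB moves by +10.0.
- The same rate change gives +77.8 at F = 390 and +83.8 at F = 420.
- From 65 to 70 bpm: +38.7, +40.7 and +41.6 at F = 390, 410 and 420, all counted as above 30. QTcB moves by about 5.

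**Change hidden by a falling rate.** A true rise from 400 to 440 while HR falls from 75 to 65 bpm gives 440 × (60/65)^(−7/6) − 400 × 0.8^(−7/6) = −35.9 msec.

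**RR entered in msec.** For QT 400 and RR 800, the printed formula gives 400/800^(3/2) = 0.02, the cube-root formula 43.1 and Bazett 14.1. No such value could reach 500, so the unit matters whichever exponent is used.

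**The case against.** The strongest reply is that this is a slip in a table footnote, or not an error in the plan at all.

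- **Extraction fault.** The case rests on one superscript. The available text mishandles such notation elsewhere: the molecular formula in Protocol Section 1 shows a carbon count of 12 where the chemical name calls for two chlorines. This stands as a reason to look at the source page first. The Bazett superscript in the same footnote reads correctly, which lowers the risk but does not remove it.
- **The method is named correctly.** The body text and the footnote both say Fridericia, so the intention is clear and many programmers would use the cube root. This stands, and it makes the harm conditional.
- **Central reader.** Protocol 6.6.5 and 6.7 send ECGs to a central reader for measurement and analysis, with data transferred to the sponsor. That makes sponsor derivation less likely. Neither section says that QTcF is among the values supplied, and the SAP speaks of calculating QTc.
- **Both directions.** Errors in both directions require RR in seconds. With RR in msec nothing would be flagged, and the QTcB output would be visibly unusable too. This is correct, and it supports stating the unit.
- **It would be noticed.** QTcF means far above the QTcB means in the same table would look implausible. That is likely, but a specification should not depend on it.
- **Limited reach.** ECGs are scheduled at only three points (Visit 1, Visit 12, Visit 31/ET), the safety analyses are descriptive, and no withdrawal criterion in Protocol 8.9 uses QTc. All true. The single-ECG examples also do not predict the PCS percentages, because of the non-PCS baseline rule.

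**Conclusion.** The concern holds. As the SAP reads, its only QTcF formula is not the Fridericia correction it names, and applying it would give wrong QTcF results everywhere except at 60 bpm. For a true QTcF of 390 to 430 msec, false flags above 500 begin at about 74 to 68 bpm, while a true 510 msec is missed below 59 bpm. A 10 bpm rise from 65 to 75 adds about 78 to 84 msec of spurious change for a true QTcF of 390 to 420.

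These sizes rest on assumed QT and heart-rate values and on RR in seconds. The harm arises only if the footnote is what is programmed. QTcB, uncorrected QT, the investigator and central cardiologist interpretations, and all efficacy analyses are unaffected. Confidence is medium, because the superscript still has to be confirmed on the source page. The error lies in the stated derivation of pre-specified safety outputs, so it should be corrected.

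**What to change.** 1. Check the exponent on the source page of SAP Table 11.4-1.
2. If it reads 3/2, change the footnote to QTcF = QT/(RR)^(1/3).
3. Whatever the source page shows, state that RR is in seconds for both QTcB and QTcF.
4. Add one sentence saying whether QTcF is derived by the sponsor or taken from the central reader. If the reader supplies QTcF, compare derived and supplied values on a sample of ECGs. This step is useful but secondary.

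The cost is one footnote and one sentence in the SAP, plus confirmation that the ECG program uses the corrected formula. No new data are needed.
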